Patients will be eligible for the study if they: 1) have been diagnosed with a new episode of depression in primary care at any of three VA study sites or associated CBOCs; 2) have a current PHQ-9 score ≥ 10 ; 3) are not receiving mental health care outside of VHA; 4) have broadband internet access at home or confirm

E.2 Study Sites and Patient Population

We have chosen our study sites, Ann Arbor, Battle Creek, Detroit), to ensure adequate numbers for the study (estimated at 330 patients, see below), patient diversity and inclusion of rural and urban areas.

All study VA medical centers have a full range of services, including primary care clinics and comprehensive (inpatient and outpatient) mental health services. These three medical centers also have a total of 9 associated Community Based Outpatient Clinics (CBOCs). The John D. Dingell VA

willingness, ability, and a plan to go to their VA or library to complete cCBT modules; 5) have familiarity with email and internet use (see below); and 6) have stable access to and ability to communicate by telephone.

[figure not shown]
We will assess patients' familiarity and self assessed comfort with the internet with questions such as "How frequently do you use the internet?" and "How often do you email?". Our threshold for being computer familiar will be relatively low, requiring only that individuals have an existing email account that they access at least once per week. In our pilot work, we found patients who met these criteria had a higher likelihood of completing the cCBT modules.

We will **include patients who have suicidal ideation** that is not immediately threatening. Suicidal ideation is common among patients in treatment for depression. Approximately 30-50% of patients in depression treatment endorse some level of suicidal ideation, although only 2-3% are a current suicide risk.(56) Peer specialists will follow the protocol used within their facility mental health services when patients confide suicidal thoughts. These protocols are clearly outlined for all staff at each of these facilities, and will be reviewed with study peer specialists during their training. The protocol for research staff when patients divulge suicidal thoughts upon screening is outlined below.

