E.7.b Choice of intervention arm: We chose the PS-cCBT as the intervention arm for several reasons. First, this intervention has synergies with ongoing operational initiatives within the VHA, providing evidence-based treatments for depression AND providing recovery-oriented services. cCBT is currently widely disseminated in the UK as an evidence-based option for depression care but needs to be supported to be most effective. Peer specialists, who constitute a rapidly growing workforce in mental health within the VHA, are ideal candidates to support this effort for reasons elucidated through out this proposal. Combining these initiatives allows us to examine, for the first time, a low cost, flexible and evidence-based treatment option (cCBT) supported in a manner that is likely to increase its effectiveness and promote patient recovery.

E.7.c Choice of location: Finally, although cCBT has been successfully piloted in specialty mental health settings and we included VA patients from specialty mental health in our pilot, we decided to focus on providing PS-cCBT for primary care patients. The body of work supporting cCBT's effectiveness for primary care patients is more robust than the literature on cCBT in specialty mental health settings. Also in our pilot, although patients in primary care showed similar reductions in depressive symptoms as patients recruited from specialty mental health, they rated the PS-cCBT intervention as more useful, relevant, and easier to use. Patients in primary care are also likely to receive fewer intensive psychotherapy services than patients treated in specialty mental health.

E.8 Patient Safety and Confidentiality Issues

E.8.a Patient safety: Threats to patient safety will consist primarily of lack of treatment response or worsening of depressive symptoms and the emergence of suicidal ideation or behaviors. We note that these threats can occur for all VA patients in depression treatment, including patients in both PS-cCBT and EUC. Patients enrolled in either arm of this study will have all the access to depression care that is usually provided to VA patients plus additional safety precautions and monitoring. **Importantly, all study patients will continue to receive usual care from their treating clinicians and have full access to these clinicians throughout the study.**

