Threats to safety of patients in this study may also arise from the study interventions. Specifically, patients in the PS-cCBT arm may become more distressed or symptomatic through working with the cCBT modules or through their interactions with peer specialists. To mitigate this possibility, all peer specialists will be supervised by clinicians who are part of the PC-MHI team, who in turn, will work in concert with Drs. [name] and [name] who will oversee peer specialists' training and activity across study sites.

Patients' clinical status will also be systematically followed in the BTB program through the use of standardized scales (an inherent part of this clinical intervention) so that clinical worsening will be readily identified. This level of symptom monitoring is as intensive as that provided in proactive care management. If patients' symptoms are increasing significantly over time (i.e. depression scores increase >25% from baseline at more than one follow up clinical assessment point), then the supervising clinician will contact the patient and discuss their treatment progress, treatment preferences, and options for increasing the intensity of treatment.

Also, at the end of PS-cCBT participation, patients who continue with problematic symptoms will be encouraged to progress on to more intensive treatments. Please note that, PS-cCBT is not designed to “replace” more intensive and proven interventions, such as face-to-face individual CBT, but to serve as a first intervention that may provide sufficient benefit but could also serve as a “stepping-stone” to more intensive care if needed.

Potentially, patients in the study may develop suicidal ideation. Again, this will be monitored as part of the cCBT program as often as in proactive care management. The cCBT program will include information about local emergency resources as well as the Veterans Crisis Line which can provide immediate assistance. Research staff will also be available in a timely fashion and will further assess the seriousness of any emerging suicidal ideation or behaviors within 48 hours. Patients’ clinicians will also be informed and asked to follow up.

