E.11.a Analyses of Success of Randomization: We will first determine the success of the randomization process for potential prognostic factors that may affect the primary outcomes of severity of depressive symptoms and functional status, but were not considered in minimization scheme. These factors include variables such as prior hospitalization or baseline severity of anxiety symptoms. Potential differences between groups will be determined through the use of t-tests or chi-square analyses, as appropriate. When there are significant differences in the distribution of these variables, they will be included as covariates in multivariable analyses. The interpretations of final results will also be made carefully in the presence of significant baseline differences.

E.11.b Analyses Relevant to Primary Aims: Primary study analyses will determine the effectiveness of the PS-cCBT intervention in decreasing depressive symptoms (IDS-SR), improving functioning and quality of life (VR-12, Q-LESQ-SF), and increasing recovery focus (RAS) at 24 weeks post-enrollment. We will also examine the impact of the intervention on depression coping efficacy and skills, antidepressant adherence, and initiation and completion of traditional in-person psychotherapy (contingent on symptoms).

Analyses will be of two broad types, those that assess intervention effects at each assessment point (12 weeks and 24 weeks), and those that determine effects over time. Primary analysis will be based on “intent to treat” principle, with all randomized patients included in the originally randomized group, regardless of whether they have subsequently dropped from their assigned treatment group.

Univariate Analyses: In the first phase of analysis (data verification), we will examine the distribution of all study variables to assess extreme values, missing data, variances, possible coding errors, skewness and whether or how to categorize skewed data. We will then describe means ($\pm SD$) for the continuous IDS-SR, VR-12, Q-LESQ-SF, and RAS measures by study group for each assessment time for the entire sample and

for each of the study sites, separately.

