Bivariate/Multivariate Analyses: We will evaluate bivariate associations between patients' treatment condition (PS-cCBT versus EUC) and the study outcomes to determine unadjusted measures of effect. We will also examine bivariate relationships between each of the potential covariates and the outcomes, and between each of the potential covariates and intervention group to assess possible confounders. Bivariate relationships between potential covariates will also be assessed for any collinearity in subsequent analyses.

Independent (Predictor) Variables	Dependent (Outcome) Variables
Treatment Group PS-cCBT vs Usual Care Potential Covariates Demographics Baseline measures of outcome variables Psychiatric comorbidities Study Site Social Support Prior to Enrollment General Primary Care Clinician Level of Depression Treatment Activity Distance to nearest VA facility	Primary Outcome Variables IDS-SR VR-12 Q-LES-Q-SF RAS Secondary Outcomes * Depression Coping skills (DCSES, CBTSQ) Antidepressant adherence Traditional psychotherapy use (contingent on symptoms) Hope Patient activation Anxiety Suicidal Ideation

* please note some secondary outcomes may be considered mediators in other study analyses

Effects At Each Assessment Time: Comparison at 24 weeks post-enrollment will be our primary comparison, but we will also assess patient outcomes to acute effects of the PS-cCBT intervention at 12 weeks. We will first obtain unadjusted differences in the outcomes between the two study groups with its associated 95% confidence interval. Comparisons of primary outcomes (IDS-SR, VR-12, Q-LES-Q-SF, RAS) between treatment groups at each assessment time will be accomplished using multiple regression models. Multiple regression models for each outcome variables will include the baseline values of the outcome variable as covariates to adjust for baseline differences, making the model analogous to analysis of covariance. We will also include two dummy variables for three sites and adjust for additional baseline covariates that show baseline imbalances in bivariate analyses.

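### The E.11 comparisons that could cover suicidal ideation net new onset against resolution, and E.11 specifies no by-arm count of new onset

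*Combined protocol and SAP*

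**What the plan says.** - **The threat.** E.8.a states: "Threats to patient safety will consist primarily of lack of treatment response or worsening of depressive symptoms and the emergence of suicidal ideation or behaviors". It adds that these can arise in either arm. Separately, it says that "patients in the PS-cCBT arm may become more distressed or symptomatic through working with the cCBT modules or through their interactions with peer specialists".
- **Who is enrolled.** E.3 will "include patients who have suicidal ideation" that is not immediately threatening, and gives the background rate: "Approximately 30-50% of patients in depression treatment endorse some level of suicidal ideation". Only immediate risk, shown by plan or intent, excludes a patient.
- **Measurement.** A suicidality scale is scheduled at baseline, 12 and 24 weeks. E.9.b describes the C-SSRS, which covers ideation and behavior; the E.10 schedule lists the BSS.
- **Analysis.** The E.11.b table lists the topic among secondary outcomes: "Hope Patient activation Anxiety Suicidal Ideation". The comparison at each assessment time begins: "We will first obtain unadjusted differences in the outcomes between the two study groups with its associated 95% confidence interval". Baseline-adjusted regressions are introduced for the four primary outcomes, then described for each outcome variable. A mixed model of outcomes at all three times follows. E.11.c states methods for coping skills, antidepressant adherence and psychotherapy, and does not mention ideation.
- **Description.** The by-arm summaries are confined to the primary scales: "We will then describe means ($\pm SD$) for the continuous IDS-SR, VR-12, Q-LESQ-SF, and RAS measures by study group for each assessment time".
- **Monitoring outside E.11.** E.8.a has a clinician-contact rule for patients in the BTB program ("depression scores increase >25% from baseline at more than one follow up clinical assessment point"). Table 3 has alerts to primary care clinicians in both arms. E.8.b promises the DSMB serious adverse event reports and summaries of all outcomes.

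**The concern.** The event that E.8.a worries about is emergence: a patient without ideation who develops it. Because a sizeable share of patients may enter with ideation, the arm difference at follow-up has two parts, new onset among those free of it and resolution among those who had it. A treatment that helps many patients and unsettles a few can raise both, and the two parts then offset each other. Adjusting for the baseline value makes the estimate more precise but, without a treatment-by-baseline interaction, still gives one net figure. A time-averaged or slope effect from the mixed model does the same.

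At stake is what the results section can say about harm. Followed as written, E.11 could report little difference in suicidal ideation although more patients had newly developed it in one arm. Protection of individual patients is not in question.

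**Working it through.** **The plan's own figure.** With 0.4 SD, two-sided alpha 0.05 and 90% power (E.13), n per arm = 2(1.960 + 1.282)² / 0.4² = 131.3, so 132. Allowing for 20% dropout, 132 / 0.8 = 165 per arm, 330 in total. This matches E.13. The plan gives no figure for suicidal ideation.

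**Inputs from the documents.** 132 assessed per arm. Baseline ideation b = 30-50%, with 40% as the midpoint. The 30-50% is quoted for depression treatment generally, so applying it to this sample is an assumption.

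**Inputs that are assumed.** Onset among patients without baseline ideation: 5% EUC, 15% PS-cCBT. Resolution in EUC: 30%. Extra resolution in PS-cCBT: d.

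**New-onset row (b = 0.4).** Patients without ideation at baseline: 132 × 0.6 = 79.2 per arm. New cases: 79.2 × 0.15 = 11.9 against 79.2 × 0.05 = 4.0. Difference +10 points. SE = √[(0.15×0.85 + 0.05×0.95)/79.2] = 0.0470, half-width 9.2 points. Chance that the interval lies above zero: Φ(0.10/0.0470 − 1.96) = 57%.

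**Follow-up prevalence, unadjusted, d = 0.** EUC 0.6×0.05 + 0.4×0.70 = 31%; PS-cCBT 0.6×0.15 + 0.4×0.70 = 37%. Difference +6.0 points. SE = √[(0.31×0.69 + 0.37×0.63)/132] = 0.0582, half-width 11.4. Chance: Φ(0.060/0.0582 − 1.96) = 18%.

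**Follow-up prevalence, adjusted for baseline ideation, d = 0.** The within-baseline-group variance is 0.6×0.05×0.95 + 0.4×0.7×0.3 = 0.1125 in EUC and 0.6×0.15×0.85 + 0.4×0.7×0.3 = 0.1605 in PS-cCBT. Fitting one common slope (0.60, where the arms have 0.65 and 0.55) adds 0.24×0.05² = 0.0006 to each. SE = √[(0.1131 + 0.1611)/132] = 0.0456, half-width 8.9. Chance: Φ(0.060/0.0456 − 1.96) = 26%.

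**Effect of extra resolution.** The prevalence difference is (1−b)×0.10 − b×d. At b = 0.4 it is +6.0, +4.0, +2.0, 0.0 and −2.0 points for d = 0, 5, 10, 15 and 20 points. The new-onset row stays at +10 throughout.

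| Chance that the 95% interval excludes zero on the harm side | b = 30% | b = 40% | b = 50% |
|---|---|---|---|
| New-onset row | 63% | 57% | 49% |
| Prevalence, unadjusted, d = 0 | 25% | 18% | 13% |
| Prevalence, baseline-adjusted, d = 0 | 36% | 26% | 18% |
| Prevalence, unadjusted, d = 10 points | 11% | 5% | 3% |

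At b = 40% and d = 10 points, baseline adjustment gives about 6% in place of 5%.

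**Missing follow-up.** Of 165 × 0.6 = 99 patients per arm without baseline ideation, 20% dropout leaves 19.8 unassessed, more than the 4 to 12 new cases.

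E.11 does not say whether ideation is compared as a proportion or a mean score. A mean-score difference would also mix onset and resolution; I have not computed it.

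**The case against.** **More than one comparison may reach ideation.** A reader might infer that the unadjusted difference is the sole arm comparison. The documents do not support that: the regressions are described for each outcome variable and the mixed model for outcomes generally, while E.11.c extends the methods by name only to other outcomes. The reach of these models is ambiguous. If the adjusted model applies, the gap to the new-onset row narrows (26% rather than 18%, against 57%). The estimate remains a net effect.

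**E.8.a does not attribute excess ideation to PS-cCBT.** A reader might join its two statements. The one about the intervention speaks of distress and symptoms; suicidal ideation is raised for study patients in both arms. An excess under PS-cCBT is a possibility worth counting, not a harm the protocol predicts.

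**Masking rests on assumed rates.** This stands. In the illustration the net difference reaches zero only if PS-cCBT triples onset and also raises resolution by 15 points (at 40% baseline ideation). With no resolution effect it already points toward harm, at +6.0 points.

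**Safety may be tabulated elsewhere.** E.8 refers to a Human Participants section that is not supplied, and the DSMB receives summaries of all outcomes. A reader might infer that the trial has no by-arm safety table at all; the documents do not show that.

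**The new row is itself imprecise.** Also true. For an 80% chance of an interval excluding zero, the excess over 5% onset must be about 13 to 16 points.

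**Conclusion.** The point holds as a gap in E.11, and a modest one. The plan names emergence of suicidal ideation as a main threat, enrols patients who already have ideation, measures it in both arms, and then specifies only comparisons that net onset against resolution. That structural point does not depend on the assumed rates.

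The size does depend on them. With onset of 15% against 5%, 30% resolution in EUC and 40% baseline ideation, a new-onset row has about a 57% chance of an interval excluding zero on the harm side. Follow-up prevalence has 18% unadjusted or 26% adjusted with no resolution effect, and 5-6% with a 10-point resolution benefit. This shows that harm could be diluted or hidden, not that it is likely to be. It is a cheap improvement to harm reporting, and it implies no fault in the monitoring of individual patients.

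**What to change.** Add to E.11.c a descriptive by-arm table at weeks 12 and 24, built from the study assessments that both arms complete:

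- New suicidal ideation (any positive ideation item) among patients with no positive ideation item at baseline, on the scale actually fielded. State whether that is the C-SSRS or the BSS. If it is the C-SSRS, add a row for new suicidal behavior.
- Counts, risk differences and 95% confidence intervals, with no significance threshold.
- By arm, the number without baseline ideation whose follow-up is missing, with no imputation in this table.
- The same table in the DSMB summaries.

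Use the scheduled assessments rather than cases noticed in care, because BTB questionnaires and peer calls occur only under PS-cCBT and would detect more cases there. I would not add a count of patients whose IDS-SR worsens: a treatment that lowers scores on average also lowers the number crossing a worsening threshold, so the count can favour PS-cCBT while a minority is harmed.

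The cost is a short paragraph and one table, with no new visits, staff or patients and no change to the sample size. The downside is precision: half-widths of about 9-10 points mean that only a large excess would be visible.

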We have attempted to keep the burden of study assessments within reason, deliberately choosing some shorter measures of important constructs, if possible. (For example, we use the GAD-7 rather than the BAI for measurement of anxiety because of its shorter length.) The estimated times for study assessments is approximately 50-60 minutes, based on published questionnaire administration times and the use of the general rule of 5 closed-ended questions or 2 open-ended questions per minute.

The Interpersonal Support Evaluation List (ISEL) will only be administered at baseline and several covariates will be assessed using chart and administrative data, reducing patient burden.

Study Measures for Patient Completion	Screening	Baseline	12 weeks	24 weeks
Screening Measures				
Patient Health Questionnaire (PHQ-9)	X			
Computer Literacy (study specific questions)	X			
Primary Outcome Measures				
Inventory of Depression Symptoms – Self Report (IDS-SR)		X	X	X
Veterans RAND 12-Item Health Survey (VR-12)		X	X	X
Quality of Life Enjoyment and Satisfaction Questionnaire		X	X	X
Recovery Assessment Scale (RAS)		X	X	X
Secondary Outcome Measures*/ Many also Mediators				
Depression Coping Self-Efficacy Scale (DCSES)		X	X	X
Cognitive-Behavioral Therapy Skills Questionnaire (CBTSQ)		X	X	X
Adherence with Antidepressant Medications (MPR* and BMQ)		X	X	X
Receipt of Traditional In-Person Psychotherapy		X	X	X
State Hope Scale (SHS)		X	X	X
Patient Activation Measure		X	X	X
Internalized Stigma of Mental Illness (ISMI)		X	X	X
Working Alliance with Peer Specialist (study specific questions)			X	X
Generalized Anxiety Disorder -7 (GAD-7)		X	X	X
Beck Scale for Suicidal Ideation (BSS)		X	X	X
Other Covariates				
Demographics		X		
Alcohol use (AUDIT-C)		X	X	X
Primary care provider mental health activity*		X		
Concurrent health services use (VA administrative data* and CSI)		X	X	X
Mental health and substance use comorbidities*		X		
General medical burden*		X		
Baseline social support (ISEL)		X		
Distance to VA facility (calculated by staff)*		X		

*calculated by staff, no burden on patient

E.11 Study Analyses

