Effects over time: We will next compare the effects of the PS-cCBT intervention versus EUC over time. This second set of analyses will use linear mixed-effects model with outcomes at all three assessment times as the response variable. The mixed-effects model will include patient as random intercepts to take into account the correlation of data within person over time. The model will allow the full use of all observed data despite missing outcomes at one or two assessment times and will give unbiased estimates as long as the missingness does not depend on the unobserved missing data (missing at random).

Using this model, we will be able to estimate the time-averaged effect of the intervention if the response to the intervention is immediate and lasting, or compare the rates of changes in the outcomes between the two groups if the outcomes show different trends between the study groups. Whether we compare the time-averaged effects or the rates between two groups, we will be guided by careful graphical exploration of the longitudinal data over time between the two groups. For example, if we find scores from IDS-SR to slowly decrease over time in the intervention group, but to slightly increase in the enhanced usual care group, we will model this by including a continuous time indicator (e.g., month since randomization) and a time by intervention group term in the model. The coefficient from the interaction term will estimate the difference in rates of change in outcomes between the two study groups.

E.11.c Secondary Outcomes: Analyses of secondary outcome of Depression Coping Skills and antidepressant medication adherence will proceed as outlined above for the primary outcome variables. For analyses of receipt of VA and non-VA traditional in-person psychotherapy, we will compare the percent

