Bivariate/Multivariable Analyses: To explore the differential effectiveness of the PS-cCBT intervention among these patient subgroups, we will extend the model to include potential moderators of the intervention effect. For example, in addition to treatment group and other covariates, we will now stratify the analysis by the categories of baseline depressive symptom severity. If there is an observed differential effect (e.g., intervention effects are larger for patients with moderate or higher levels of depression symptoms than those with mild symptoms), then the differential effect of the PS-cCBT for these subgroups will be more formally assessed by adding in the main and interaction effects of the moderator (e.g., depressive symptom categories) and the intervention group. Assessment of whether the effects of PS-cCBT depend on the primary care provider's level of depression management activity will be carried out in similar fashion. Because subgroups are being considered, we may have limited power to detect differential effects of the intervention unless the interaction is large, and at the same time, due to the limited power, we may find that benefit from PS-cCBT does not depend on baseline severity of depressive symptoms. Therefore, these analyses will be exploratory and focused more on identifying trends rather than inferential testing.

E.12 Approach to Missing Data: Our initial analyses will only use observed data. We will check if missingness depends on covariates and will include those covariates in the models described above. However, we will conduct a second analysis that imputes missing data. Specifically, we will impute missing data using the method described by Lavori, Dawson, and Shera.(83) In brief, we will use logistic regression to model patients' likelihood of having specific outcome data and define strata within which outcome values are missing

at random. We will then stratify patients according to these propensities and randomly sample from the observed outcome distribution and impute values for missing data within each stratum. When data are missing for items within scales, we will use recommended imputation procedures rather than deleting patients list-wise from the analysis.

E.13 Power Analysis

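### Four outcomes are primary without ranking, with no error control across them and no definition of a positive trial; E.13's .05 and 90% power cover depressive symptoms only

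*Combined protocol and SAP*

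**What the plan says.** **Which outcomes are primary.** E.11.b opens: "Primary study analyses will determine the effectiveness of the PS-cCBT intervention in decreasing depressive symptoms (IDS-SR), improving functioning and quality of life" (VR-12 and Q-LES-Q-SF), and adds recovery focus (RAS), all at 24 weeks. Its variables table reads "Primary Outcome Variables IDS-SR VR-12 Q-LES-Q-SF RAS Secondary Outcomes". The E.10 schedule puts the same four under its primary heading, and E.11.d names the same four constructs. Each outcome gets its own baseline-adjusted regression with site terms.

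**Where the text differs.** E.11.a names two primary outcomes, depressive symptoms and functional status. E.11.e describes the primary comparisons as quality of life and functional status, leaving depressive symptoms out. E.9.a also places AUDIT-C under the primary heading, while E.10 lists it as a covariate.

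**Time point and order of analyses.** The time point is fixed: "Comparison at 24 weeks post-enrollment will be our primary comparison". E.11.b begins descriptively, "We will first obtain unadjusted differences in the outcomes between the two study groups with its associated 95% confidence interval", and then assigns the primary comparisons to the regressions: "Comparisons of primary outcomes (IDS-SR, VR-12, Q-LES-Q-SF, RAS) between treatment groups at each assessment time will be accomplished using multiple regression models". Next, "This second set of analyses will use linear mixed-effects model with outcomes at all three assessment times as the response variable". E.12 says "Our initial analyses will only use observed data" and describes imputation as a second analysis.

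**Alpha and power.** E.13 sizes the trial at 330 patients for 90% power on depressive symptoms at 24 weeks, with 0.4 SD, two-tailed .05 and 20% dropout. It gives no power for VR-12, Q-LES-Q-SF or RAS. Section F makes a possible addition to the VA peer-specialist manual depend on a positive trial, without defining one.

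**The concern.** With four unranked primary tests and .05 as the only alpha given, success could be read in three ways: any one outcome, all four, or IDS-SR alone. The false-positive risk and the power of the trial differ widely between these readings, and the choice could be made after the results are seen. E.13 does not settle it. Its 90% for depressive symptoms is valid under any rule that tests IDS-SR at .05, whatever is done with the other three.

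**Working it through.** **Inputs.** From E.13: 0.4 SD, two-sided .05, 90% power, 20% dropout, 165 per arm. From E.10 and E.11.b: four primary outcomes. Assumed, because the documents give no figures: a common pairwise correlation r between the four test statistics, from 0 to .9; a .05 level for the three outcomes that E.13 does not cover; and, in one scenario, a 0.2 SD effect on those three.

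**1. The plan's own figure.** n per arm = 2(z₀.₉₇₅ + z₀.₉₀)²/δ² = 2(1.960 + 1.282)²/0.4² = 131.3, so 132. Then 132/0.80 = 165 per arm, 330 in total. The expected z is 0.4 × √(132/2) = 3.25, and the power is Φ(3.25 − 1.96) = 90.1% (89.9% by t-test). E.13 reproduces for one outcome.

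**2. Any one of four at .05, no true effect.** If independent, at least one significant result has probability 1 − .95⁴ = 18.5%, and at least one favouring PS-cCBT has 1 − .975⁴ = 9.6%. Correlated cases come from 1,000,000 draws of four equally correlated normal statistics.

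**3. All four required, 132 completers per arm.** With 0.4 SD on each and independence, power is .901⁴ = 66%. The expected z for 0.2 SD is 1.62.

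| | r = 0 | .5 | .7 | .9 |
|---|---|---|---|---|
| Any of four: two-sided familywise error | 18.5% | 15.6% | 13.0% | 9.3% |
| Any of four: falsely favourable | 9.6% | 7.8% | 6.5% | 4.7% |
| All four: power, 0.4 SD on each | 66.1% | 74.4% | 78.6% | 83.8% |
| All four: power, 0.4 SD on IDS-SR, 0.2 SD on the rest | 4.5% | 14.5% | 19.6% | 26.9% |

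**4. IDS-SR first, then Holm on the other three.** If IDS-SR has no true effect, any claim first needs a false rejection there, at most 5%. If it has an effect, Holm holds the other three at 5% overall. Familywise error is therefore at most 5%, and IDS-SR power stays at 90%. With a true 0.4 SD on all four, another outcome reaches .05 while IDS-SR does not in 9.8%, 9.0%, 7.7% and 5.0% of trials (r = 0, .5, .7, .9).

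**5. Equal rank instead.** Bonferroni gives .05/4 = .0125 each, critical z 2.498. IDS-SR power is Φ(3.25 − 2.498) = 77.4%. Restoring 90% needs 2(2.498 + 1.282)²/0.4² = 178.5, so 179 completers per arm; 179/0.80 gives 224 enrolled per arm, 448 in total. Under Holm across four, at the same values of r, IDS-SR power is 87.4%, 85.3%, 84.4% and 82.8% with 0.4 SD on all, and 79.4%, 78.1%, 77.6% and 77.4% with 0.2 SD on the other three.

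**The case against.** The best defence is that IDS-SR is already primary in effect: the trial is sized on depressive symptoms, and IDS-SR heads each list of the four. That is a real hint, but a basis for sample size is not a decision rule, and E.11.e points the other way by omitting depressive symptoms from the primary comparisons. E.13 also names the construct, not the scale.

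Second, the supplied text begins at section E, so an aims or hypotheses section might contain a ranking. This limits the claim to what was supplied. Even so, the analysis section should carry the rule.

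Third, a reader might infer that the deciding analysis is open among unadjusted, adjusted, mixed-model, observed-data and imputed results. The documents do not support that. E.11.b assigns the primary comparisons to the adjusted 24-week regressions and calls the mixed model a second set; E.12 puts observed data first and imputation second. What stays open is the final covariate set: E.11.a and E.11.b add covariates that show imbalance, E.12 adds those related to missingness, and E.9.d adds clinician activity.

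Fourth, section F's reference to a positive trial concerns dissemination, not inference. That is fair, but no other passage supplies the criterion.

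**Conclusion.** The concern holds for the supplied text: four unranked primary outcomes, inconsistent lists elsewhere, no error control across them and no success criterion. Because the missing rule governs the trial's main conclusion, it should be settled before outcomes are compared by arm.

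The size depends on the reading. If any single hit counted, familywise error would be roughly two to four times the nominal 5%, and the falsely favourable rate also two to four times 2.5%, over assumed correlations of 0 to .9. A reader might infer that the plan operates at 18.5% error. It does not say so: no passage states that one hit suffices, and 18.5% also needs independence and counts results in either direction. Nor is the sample size wrong; 330 is correct for the one outcome it covers. The all-four power figures are equally conditional, since E.13 supports 0.4 SD only for depressive symptoms and 0.2 SD is an assumption.

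A subsidiary point, which adds nothing to these figures: E.9.a lists eight VR-12 domains, and no section names the score to be tested.

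**What to change.** Add to E.11.b, dated before outcomes are compared by arm:

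- The 24-week IDS-SR regression, adjusted for baseline IDS-SR and site, is tested at two-sided .05 and alone defines a positive trial.
- If it is significant, one named VR-12 score, Q-LES-Q-SF and RAS at 24 weeks are tested by Holm at overall .05. Otherwise they are reported with 95% intervals as non-confirmatory.
- State whether the imbalance covariates (E.11.a, E.11.b) and missingness covariates (E.12) enter the decisive model or a supportive one, and do the same for clinician activity (E.9.d).
- State how the observed-data analysis relates to E.11.b's commitment to include everyone randomised.

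Then reconcile E.9.a (AUDIT-C), the E.10 and E.11.b tables, E.11.a and E.11.e with this ranking.

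**Cost.** Wording in several sections, with no change to enrolment, data collection or the stated power. The price is that three outcomes become subordinate: with a true 0.4 SD on all four, about 5-10% of trials (r = .9 to 0) would show an effect elsewhere but not on IDS-SR. The documents do not say whether data collection is complete; a rule set after comparison by arm would not control error.

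**Alternative.** If the four must keep equal rank, use Holm or Bonferroni across all four and restate IDS-SR power at 330 patients: about 77% under Bonferroni; under Holm 83-87% if all four effects are 0.4 SD, or 77-79% if the other three are 0.2 SD.
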